Clinical laboratory data consist of chemistry, hematology, and hormonal tests. Only data collected by the central laboratory will be used to do the analyses.

The incidence of vasomotor symptoms as assessed through adverse event reporting will be summarized by the study treatment arm.

Bone mineral density data will be collected and analyzed by the central radiology laboratory including bone mineral content (g), bone area (area, cm²), and bone mineral density (g/cm²) each for L1, L2, L3, L4, total hip, and femoral neck, and average bone mineral density of L1-L4 (lumbar spine), Z-score for bone mineral density lumbar spine (L1-L4), total hip, and femoral neck.

All BMD data will be listed and summarized by visit. The change, percent change from study Week 52/Baseline to Weeks 76 and 104 and associated 95% CIs will be presented by the study treatment group for each bone mineral density parameter. The number and percentage of patients meeting a bone mineral density decline of at least 3%, 4%, 5%, 6%, or 7% by body area (lumbar spine, total hip, or femoral neck) will be estimated with 95% CIs by the study treatment group.

Additional analyses will be performed to exam the correlation between bone mineral density loss with demographic and baseline characteristics and with treatment exposure. Details will be provided in the SAP.

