9.3.3.1. Analysis Using Week 52/Baseline Bone Mineral Density as Baseline

As defined in Section 4.3.6, the BMD at Week 52 of the extension study will be used as the Week 52/Baseline in the randomized withdrawal study as long as it was within 30 days of the first dose date of the randomized study drug. If there are multiple BMD measurements at Week 52 in the extension study, the one closest to the first dose date of the study drug will be used as Week 52/Baseline in the randomized withdrawal study.

BMD at Week 52/Baseline and Week 104 visit will be summarized descriptively by treatment group and each measured anatomical location for all patients in the safety population. Percentage changes from Week 52/Baseline along with 95% CIs of mean percentage changes also will be summarized by treatment group and anatomical location. Mean percentage change from Week 52/Baseline with its corresponding 95% CI will be plotted by visit, treatment group, and anatomical location.

An analysis of covariance (ANCOVA) model will be used to assess BMD at Week 104. The model will include treatment, stratification factors (menstrual blood loss volume at pivotal study baseline, and duration of relugolix exposure prior to randomization), race (African American versus Other) as fixed factors, and age at Week 52/Baseline, Week 52/Baseline BMD value, and BMI at Week 52/Baseline as covariates. Least square means on each anatomical location will be presented and plotted with associated 95% CIs. Taking into consideration of the BMD data collected for patients who prematurely discontinued prior to Week 104, the ANCOVA model analysis will also be performed similarly to assess BMD at Week 104/EOT.

Categorical representation of percentage change from Week 52/Baseline to Week 104 (also Week 104/EOT) will be presented by the number and proportion of patients who had BMD increase $> 0\%$, no change (0%), declines of $\leq 2\%$, $>2\%$ to 3% , $> 3\%$ to 5% , $> 5\%$ to 8% , and $> 8\%$ by pivotal study treatment group and anatomical location. The 95% CIs will be provided for the respective proportions.

Categorical changes from Week 52/Baseline in overall BMD (defined as lumbar spine and total hip) also will be assessed. Femoral neck evaluates a smaller area of bone mass than the total hip and is prone to lower precision in the measurement (Leslie et al. 2007; ISCD 2015). Since

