9.3.3.2. Analysis Using the Pivotal Study Baseline Bone Mineral Density as Baseline

For the visits in pivotal and extension studies, the visit window specified in the extension study SAP Table 3 will be used where the first dose of pivotal study drug was used as the reference.

Percentage changes from pivotal study baseline along with 95% CIs of mean percentage changes since first dose of the pivotal study drug at all the timepoints when BMD was scheduled to be collected in a pivotal study, extension study and the randomized withdrawal study also will be summarized by treatment group and anatomical location. Mean percentage change from pivotal study baseline with its corresponding 95% CI will be plotted by visit, treatment group, and anatomical location.

Categorical representation of percentage change from pivotal study baseline to all the timepoints where BMD was scheduled to be collected since pivotal study baseline will be presented by the number and proportion of patients who had BMD increase $> 0\%$, no change (0%), declines of $\leq 2\%$, $> 2\%$ to 3% , $> 3\%$ to 5% , $> 5\%$ to 8% , and $> 8\%$ by treatment group and anatomical location. The 95% CIs will be provided for the respective proportions.

Categorical changes from pivotal baseline in overall BMD (defined as lumbar spine and total hip) also will be assessed at all the timepoints where BMD was scheduled to be collected since pivotal study baseline.

Corrected BMD Z-scores and its change from pivotal study baseline will be summarized by treatment group, visit, and anatomical location with descriptive statistics including 95% CIs, and the number and percentage of patients with a corrected BMD Z-score < -2.0 will be presented by treatment group, visit, and anatomical location. Additionally, categorical change from pivotal study baseline in Z-score will be summarized as ≥ 0 , < 0 to -0.25 , < -0.25 to -0.5 , < -0.5 to -0.75 , < -0.75 to -1 , < -1 to -2 and < -2 , by treatment group, visit and anatomical location.

These analyses will be carried out by six combined analysis groups where the pivotal study treatment group, LTE study treatment and the randomized withdrawal study treatment group are considered (see the [Table 20](#) below).

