In addition, to observe the long-term impact of relugolix + delayed E2/NETA on BMD loss, these analyses will be performed by the relugolix monotherapy status groups: patients who were previously treated with any relugolix + delayed E2/NETA (from Groups 3 and 4) and the rest of the patients (from Groups 1, 2, 5 and 6).

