9.3.3.3. Analysis Using Pivotal Week 12 BMD as Baseline

To observe the long-term impact of relugolix+E2/NETA on BMD loss in dependent of hypoestrogenic effect caused by relugolix monotherapy, BMD at Week 12 in the pivotal studies will be used as baseline to calculate percent change in BMD for each patient. Descriptive statistics will be provided for percent change from pivotal Week 12 in BMD by the six combination groups and as well as by the monotherapy status groups.

Table 20: Combined Analysis Groups for Bone Mineral Density

Combined Analysis Group	Pivotal Study Treatment Group	Extension Study Treatment	Randomized Withdrawal Study Treatment Group
Group 1 Relugolix + E2/NETA Relugolix + E2/NETA Relugolix + E2/NETA	Relugolix + E2/NETA	Relugolix + E2/NETA	Relugolix + E2/NETA
Group 2 Relugolix + E2/NETA Relugolix + E2/NETA Placebo	Relugolix + E2/NETA	Relugolix + E2/NETA	Placebo
Group 3 Relugolix + Delayed E2/NETA Relugolix + E2/NETA Relugolix + E2/NETA	Relugolix + Delayed E2/NETA	Relugolix + E2/NETA	Relugolix + E2/NETA
Group 4 Relugolix + Delayed E2/NETA Relugolix + E2/NETA Placebo	Relugolix + Delayed E2/NETA	Relugolix + E2/NETA	Placebo
Group 5 Placebo Relugolix + E2/NETA Relugolix + E2/NETA	Placebo	Relugolix + E2/NETA	Relugolix + E2/NETA
Group 6 Placebo Relugolix + E2/NETA Placebo	Placebo	Relugolix + E2/NETA	Placebo

Patients who prematurely discontinued from the study treatment after Week 60 will undergo another bone densitometry scan at the safety follow-up visit. Patients with a BMD loss of $\geq 7\%$ at lumbar spine, total hip, or femoral neck at their Week 104/Early Termination visit relative to pivotal study baseline measurement will undergo another bone densitometry scan at 6 (± 1) months and follow-up to evaluate recovery per the protocol. All available post-treatment follow-up BMD data will be listed. BMD data collected during the additional safety follow-up period may be summarized and reported in an addendum to the CSR if deemed necessary.

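### The Week 52 to Week 104 BMD-loss categories are tabulated by pivotal-study arm, so that table cannot compare relugolix with placebo over the added year

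*SAP*

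**What the plan says.** SAP Section 9.3.3.1 uses Week 52/Baseline as the reference. Mean change is by arm: "Percentage changes from Week 52/Baseline along with 95% CIs of mean percentage changes also will be summarized by treatment group and anatomical location". Z-scores and their categories are also by treatment group, and the ANCOVA at Week 104 and Week 104/EOT fits treatment. The exception is the table of percentage-change bands (gain, no change, and losses cut at 2%, 3%, 5% and 8%), which is to be shown "by pivotal study treatment group and anatomical location".

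Protocol Section 9.5 says that the number and percentage of women with a decline of at least 3%, 4%, 5%, 6% or 7% "will be estimated with 95% CIs by the study treatment group". In the protocol the study treatment groups are Group A (relugolix) and Group B (placebo).

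SAP Section 9.3.3.2 repeats the bands from the pivotal baseline by treatment group, and then adds: "These analyses will be carried out by six combined analysis groups". Each of the six is a sequence of arms across all three studies. To show the long-term effect of relugolix with delayed E2/NETA, it sets Groups 3 and 4 against "the rest of the patients (from Groups 1, 2, 5 and 6". Section 9.3.3.3 reuses that split with pivotal Week 12 as baseline. Table 20 shows that Groups 5 and 6 were pivotal-placebo women, for example "Group 6 Placebo Relugolix + E2/NETA Placebo".

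On retreatment, SAP Section 4.2.3 counts a woman as relugolix in safety analyses if she took relugolix in the randomized treatment period, and Section 4.3.5 makes open-label retreatment a separate period. A rule under Table 3 (Section 4.3.7) drops BMD scans taken more than 60 days after the last dose of study drug.

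**The concern.** BMD is the one safety measure named alongside adverse events in the study's safety objective. A mean can hide a minority with marked loss, and the band table is what would show such a minority. Grouped by pivotal arm, it describes women by what they took before Week 24 of the programme, while the change being counted happened after Week 52 under a new random allocation.

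The second issue is what the delayed-E2/NETA contrast measures. Its reference group includes women who took placebo throughout the pivotal study, so a difference could reflect early relugolix without add-back, a shorter time on relugolix, or both.

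The third is a gap. Placebo women whose heavy bleeding returns may go back on open-label relugolix for the rest of the 52 weeks, and Section 9.3.3 does not say how their scans are treated.

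**Working it through.** The plan states no BMD figure to reproduce. The one planning figure used is the 40% placebo responder rate in SAP Section 2.2. Its power statement is sound: 60% against 40% with 144 per arm (180 less 20% dropout) gives 92.8%, consistent with at least 90%.

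**1. Grouping of BMD summaries, side by side**

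| Place | Summary | Grouped by |
|---|---|---|
| Protocol 9.5 | proportions with BMD decline | this study's treatment |
| SAP 9.3.3.1 | mean percentage change, plots, Z-scores | treatment group |
| SAP 9.3.3.1 | ANCOVA | treatment as a factor |
| SAP 9.3.3.1 | percentage-change bands | pivotal arm |
| SAP 9.3.3.2 | same bands, pivotal baseline | treatment group, then six combined groups |

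The band table in 9.3.3.1 is the only one that names the pivotal arm alone.

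**2. What the pivotal-arm columns would show.** With 1:1 allocation, the expected proportion in a column is 0.5 × p(relugolix) + 0.5 × p(placebo). The rates below are assumed, for illustration:
- 5% and 15%: 0.5 × 5 + 0.5 × 15 = 10%.
- 10% and 20%: 15%.
- 20% and 10%: 15%.

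The last two cases have opposite treatment effects and give the same column.

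**3. Scheduled relugolix weeks by Week 104, ignoring retreatment** (24 pivotal, 28 extension, 52 in this study; Table 20)
- Groups 1 and 3: 24 + 28 + 52 = 104. Groups 2 and 4: 24 + 28 = 52. Group 5: 28 + 52 = 80. Group 6: 28.
- With 1:1 allocation, Groups 3+4 average (104 + 52)/2 = 78, Groups 1+2 also 78, and Groups 5+6 (80 + 28)/2 = 54.
- If Groups 5+6 are a share s of the reference group, its mean is 78 − 24s. For s = 1/3, 1/2 and 2/3 (assumed; the documents give no split) this is 70, 66 and 62, a gap of 8, 12 or 16 weeks. Restricting the reference to Groups 1+2 makes the gap zero.
- From pivotal Week 12, 12 pivotal weeks remain. Groups 1 to 4 average (92 + 40)/2 = 66 and Groups 5+6 still 54, so the gap is 12s: 4, 6 or 8 weeks. In Groups 5 and 6 this baseline precedes any relugolix; in Groups 1 to 4 it does not.

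**4. Retreatment.** A 40% responder rate leaves 60% non-responders: 0.6 × 180 = 108, or 0.6 × 144 = about 86 after dropout. Mean weeks on relugolix in the placebo arm = share retreated × (52 − start week). With 40% to 80% retreated, starting at week 8 to 24 (both assumed), this runs from 0.4 × 28 = 11.2 to 0.8 × 44 = 35.2 of 52 weeks.

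The 60-day rule can be read in two ways. SAP Sections 4.3.1 to 4.3.5 use study drug for the randomized product and retreatment drug for the open-label one. On that reading, a scan on target Day 365 is dropped if the last randomized dose was before Day 305 (365 − 60). SAP Section 2.1 calls the open-label product study drug too. On that reading the scan stays, under Placebo.

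**The case against.** The strongest reply is that the error is one phrase in one table. Drug against placebo over the added year remains visible in the means, plots, Z-scores and ANCOVA. That stands, and it limits the point. It does not rescue the table, because none of those outputs gives the proportion on each arm with a given percentage loss from Week 52. The six-group bands in 9.3.3.2 do separate the arms, but they count loss from the pivotal baseline. If grouping by prior treatment was intended, the SAP does not say so, and it departs from Protocol 9.5.

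On the contrast, Groups 3 and 4 are exactly the women given delayed E2/NETA. The comparison is descriptive, and the six groups are also shown separately, so a reader can already set 3+4 against 1+2. In the Week 52-baseline analyses, prior exposure (28 or 52 weeks) is an ANCOVA factor and a Table 19 subgroup. All of this stands, so the gain is modest. The gap in step 3 is in weeks of exposure; its effect on BMD is not quantified.

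On retreatment, labelling women by randomized arm is standard. SAP Section 1.1 says Table 1 endpoints are in general also analysed over randomized treatment plus retreatment, and Section 4.2.4 allows selected safety data in a Retreatment population. Neither states a rule for BMD scans. A split by retreatment conditions on relapse after randomization and would have small cells.

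**Conclusion.** The band table in SAP 9.3.3.1 is wrong as written and should be corrected. This rests on the text and the 1:1 allocation alone. The reference group in the delayed-E2/NETA contrast is a secondary point: 8 to 16 weeks of scheduled exposure from the pivotal baseline, under assumed shares and ignoring retreatment. The retreatment rule is an optional clarification.

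A reader might infer more than the documents support:
- *That the BMD plan as a whole does not follow treatment.* The other Week 52-baseline summaries that name a group use this study's treatment.
- *That the placebo group is largely women back on relugolix.* The documents do not give the share retreated. The planned rate suggests up to about 60% could relapse, but some non-responders may be dropouts and women may decline retreatment.
- *That the SAP dropped the protocol's exposure analysis.* Protocol 9.5 says: "Additional analyses will be performed to exam the correlation between bone mineral density loss with demographic and baseline characteristics and with treatment exposure". The SAP covers age, race, BMI and exposure before randomization; only exposure after Week 52 is not analysed.

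These are safety summaries. The primary efficacy test is unaffected.

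**What to change.** 1. In SAP 9.3.3.1, group the percentage-change bands (Week 104 and Week 104/EOT) by randomized withdrawal study treatment group, under the as-treated rule of Section 4.2.3. Apply the same grouping to the overall BMD categories that follow, which name no group. Cost: one phrase.
2. In 9.3.3.2 and 9.3.3.3, compare Groups 3+4 with Groups 1+2 and show Groups 5+6 separately. Cost: a relabelled table.
3. Optional: state how BMD scans after retreatment are handled, and whether study drug in the 60-day rule includes the open-label product. If wanted, add a descriptive summary by retreatment status or by weeks on relugolix after Week 52, labelled as post-randomization, and keep the ANCOVA by arm. Cost: a sentence and a few rows with small cells.

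No new data are needed. Make the changes before unblinding; a change to the approved plan should be noted in the clinical study report, as SAP Section 1 provides.

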9.3.3.2. Analysis Using the Pivotal Study Baseline Bone Mineral Density as Baseline

For the visits in pivotal and extension studies, the visit window specified in the extension study SAP Table 3 will be used where the first dose of pivotal study drug was used as the reference.

Percentage changes from pivotal study baseline along with 95% CIs of mean percentage changes since first dose of the pivotal study drug at all the timepoints when BMD was scheduled to be collected in a pivotal study, extension study and the randomized withdrawal study also will be summarized by treatment group and anatomical location. Mean percentage change from pivotal study baseline with its corresponding 95% CI will be plotted by visit, treatment group, and anatomical location.

Categorical representation of percentage change from pivotal study baseline to all the timepoints where BMD was scheduled to be collected since pivotal study baseline will be presented by the number and proportion of patients who had BMD increase $> 0\%$, no change (0%), declines of $\leq 2\%$, $> 2\%$ to 3% , $> 3\%$ to 5% , $> 5\%$ to 8% , and $> 8\%$ by treatment group and anatomical location. The 95% CIs will be provided for the respective proportions.

Categorical changes from pivotal baseline in overall BMD (defined as lumbar spine and total hip) also will be assessed at all the timepoints where BMD was scheduled to be collected since pivotal study baseline.

Corrected BMD Z-scores and its change from pivotal study baseline will be summarized by treatment group, visit, and anatomical location with descriptive statistics including 95% CIs, and the number and percentage of patients with a corrected BMD Z-score < -2.0 will be presented by treatment group, visit, and anatomical location. Additionally, categorical change from pivotal study baseline in Z-score will be summarized as ≥ 0 , < 0 to -0.25 , < -0.25 to -0.5 , < -0.5 to -0.75 , < -0.75 to -1 , < -1 to -2 and < -2 , by treatment group, visit and anatomical location.

These analyses will be carried out by six combined analysis groups where the pivotal study treatment group, LTE study treatment and the randomized withdrawal study treatment group are considered (see the [Table 20](#) below).

In addition, to observe the long-term impact of relugolix + delayed E2/NETA on BMD loss, these analyses will be performed by the relugolix monotherapy status groups: patients who were previously treated with any relugolix + delayed E2/NETA (from Groups 3 and 4) and the rest of the patients (from Groups 1, 2, 5 and 6).

